9. SCORING

9.1 ANNE™ Sleep Scoring

The data from ANNE™ will be reviewed and scored for respiratory events by three (3) registered polysomnography technicians (RPSGT) who are blinded to the scoring of the HST, and represent scorers in clinical practice in AASM accredited sleep disorder centers. An average will be taken of the three scores. In order to minimize interscorer variability, the technicians will have >85% concordance. To ensure quality and reproducibility, a board certified sleep medicine physician who is blinded to the experimental condition will review all raw HST data. If AHI determined from ANNE™ Sleep exhibits greater than 15% difference between three RPSGTs, a board-certified sleep medicine physician will provide the final determination of the AHI for ANNE Sleep.

Scoring of ANNE™ Sleep data will follow guidelines established by the American Academy of Sleep Medicine Manual for the Scoring of Sleep and Associated Events (v2.6)⁶. Sleep scoring includes the following variables: total sleep time (TST= the total amount of sleep time scored during the total recording time in minutes). The scoring of respiratory events to evaluate for sleep disordered breathing will also follow AASM scoring rules.

The ANNE™ Sleep will be scored similarly with the system’s onboard sensors as an alternative hypopnea and apnea sensor via PAT. The definition of mild, moderate, or severe obstructive sleep apnea is based on AHI.

- AHI < 5: Normal
- AHI ≥ 5 – <15: Mild
- AHI ≥15 – <30: Moderate
- AHI ≥ 30: Severe

The AHI calculated from ANNE™ Sleep will be considered an estimation of AHI, coined as AHI.

An apnea event is defined as:

STU#: STU00214445

- A drop in peak signal excursion by $\geq 90\%$ of pre-event baseline for ≥ 10 seconds using an oronasal thermal signal, PAP device flow, or an alternative apnea sensor.
- No requirement for a desaturation or an arousal

Hypopnea will be defined by:

- The peak signal excursions drop by $\geq 30\%$ of pre-event baseline using nasal pressure (diagnostic study), PAP device flow (titration study), or an alternative hypopnea sensor (diagnostic study)
- The duration of the $\geq 30\%$ drop in signal excursion is ≥ 10 seconds
- There is a $\geq 4\%$ oxygen desaturation from pre-event baseline and/or the event is associated with an arousal

The scoring of respiratory events to evaluate for sleep disordered breathing will also follow AASM scoring rules. Apnea-hypopnea index will be used to determine the presence and severity of sleep apnea ($AHI = \text{apneas} + \text{hypopneas} * 60 / \text{TRT}$).

The accuracy (sum of the number of true positives and true negatives divided by the sum of the number of true positives, true negatives, false positives, and false negatives), sensitivity, specificity, positive predictive value, and negative predictive value of the ANNE™ Sleep to detect moderate to severe obstructive sleep apnea will be compared to outputs from WatchPAT ONE. A Bland-Altman plot will be generated with 95% confidence to intervals to assess agreement.

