3.0 Scoring Procedure

3.1 Data Flow Overview

The high-level data flow is shown below (Figure 4). After the patient has received the ANNE Sleep system and successfully finished their sleep night data collection, the data is downloaded from the sensors and automatically uploaded to the ANNE Sleep Hub. In the ANNE Sleep Hub, the data collected from the ANNE sensors are processed and converted into an EDF format file so that it can be consumed by EDF viewers and scoring platforms such as EnsoSleep. After the dataset has been scored, the scored data is transferred back to the ANNE Sleep Hub for sleep report generation. The report generated can then be reviewed by a Healthcare Professional (HCP) to aid in the evaluation of sleep-related breathing disorders.

STU#: STU00214445

[figure not shown]

Figure 4: ANNE Sleep Data Flowchart

pAHI (peripheral arterial tonometry AHI) is calculated by counting the number of sleep-disordered breathing events for the patient divided by the TST (total sleep time). TST is automatically calculated in ANNE Sleep Hub using pulse rate.

$$pAHI = \frac{\text{Total Number of Disordered Breathing Events}}{\text{Total Sleep Time (hrs)}}$$

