3.2 Detecting Sleep Disordered Breathing Events with ANNE Sleep System

Respiratory events (Apnea episodes) are caused either by an upper airway obstruction following the collapse of the upper airway wall or central dysfunction in which the brain doesn’t send proper signals to the muscles that control breathing. During the apnea episodes, sympathetic activation causes vasoconstriction and acceleration of the heart rate. This results in attenuation of the PAT signals. PAT amplitude may vary due to reasons other than apnea events such as periodic limb movements or spontaneous arousals. This section described the steps necessary to differentiate the true respiratory event resulting in attenuation of the PAT signal and the ones caused by events not related to it.

[figure not shown]

Figure 14: Typical pattern of PAT Amp attenuation and HR increase

STU#: STU00214445

When scoring for sleep-disordered breathing (SDB) events, the first step is to see if the area that is being analyzed has (1) motion artifact or (2) body position change. If there are any of the two signals, do not continue on to see if it is an SDB event.

Next, look at the **Accel Vertical** and **Accel Horizontal** signal for chest movement reduction. If the amplitude of **both** signals drops by 90% or more for more than 10 seconds, it is categorized as an SDB event. If one or both signals does not look as below, move to analyze the attenuation of the PAT signal. Label the event as an SDB regardless of the limb sensor output.

[figure not shown]

Figure 15: Chest Movement Reduction Example

If there are motion artifacts in between the chest movement reduction, do not grade the signal as SDB. An example of it is shown below. This is usually created as part of changing the body position and should be disregarded.

STU#: STU00214445

[figure not shown]

Figure 16: Motion Artifact example

After analyzing the two accelerometer signals and concluding that there is no chest movement reduction, proceed to analyze attenuation of the PAT signal, heart rate increase, and SpO2 drop. PAT attenuation can be easily identified by seeing the PAT amplitude signal drop. Also, heart rate should increase by at least 3 bpm within 15 seconds, and the SpO2 should drop by at least 3% within 60 seconds. If the conditions above are met, label the event as SDB.

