If there is a reduction in PAT amplitude and an increase in heart rate but the SpO2 drop is not present, look at the snoring signal. If the area of interest has no snoring but there is snoring before that point, label the event as SDB.

A flow diagram is shown below to summarize the steps necessary to label SDB events using ANNE Sleep.

STU#: STU00214445

[figure not shown]

Figure 17: Flow for detection Sleep Disordered Breathing

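### Protocol Section 9.1 and the ANNE Scoring Manual define the ANNE index by different hypopnea-type event rules and different denominators (TRT versus TST), and no supplied text reconciles them

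*Combined protocol and SAP*

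**What the plan says.** **Protocol, 9.1 ANNE Sleep Scoring.** A hypopnea needs a signal fall of at least 30% for at least 10 seconds, confirmed by this condition: "There is a $\geq 4\%$ oxygen desaturation from pre-event baseline and/or the event is associated with an arousal". Apneas and hypopneas are then combined over TRT: "AHI = \text{apneas} + \text{hypopneas} * 60 / \text{TRT". The section says that ANNE recordings are scored under AASM rules with PAT as the substitute respiratory sensor. It treats the ANNE value as an estimate of AHI and applies cut-offs of 5, 15 and 30 per hour to it.

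**ANNE Scoring Manual, 3.2 Detecting Sleep Disordered Breathing Events.** Where chest movement is not reduced, the scorer looks for PAT attenuation, and "heart rate should increase by at least 3 bpm within 15 seconds, and the SpO2 should drop by at least 3% within 60 seconds". When the SpO2 fall is missing, a second route applies: "If the area of interest has no snoring but there is snoring before that point, label the event as SDB". Segments with motion artifact or a change of body position are set aside at the start: "If there are any of the two signals, do not continue on to see if it is an SDB event".

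**ANNE Scoring Manual, 3.1.4 and 3.1.** Every event gets the same label, with no separation of apnea from hypopnea. The index, called pAHI, is the event count "divided by the TST (total sleep time). TST is automatically calculated in ANNE Sleep Hub using pulse rate".

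The manual's introduction addresses it to the technicians and physicians who score ANNE recordings. Section 9.1 does not cite the manual, and the manual text supplied does not cite Section 9.1.

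**The concern.** Both texts tell scorers how to turn an ANNE recording into the number that Section 9.1 classifies at 15/h, and they do so differently. A recording near the cut-off can be moderate under one text and mild under the other.

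At stake are:
- the agreement outcome for moderate to severe OSA on the concurrent night, one of the three primary outcomes in Section 4.1;
- sensitivity, specificity, predictive values, accuracy and the Bland-Altman comparison in Section 9.1;
- diagnostic yield over several nights, the first objective in Section 2;
- the descriptive statistics by diagnosis in Section 10.2.

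Night-to-night variation in AHI remains internally comparable if one rule is used throughout. The usability outcome is not affected.

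**Working it through.** **Step 1: the two texts side by side.**

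| Element | Protocol 9.1 | Scoring Manual |
|---|---|---|
| Apnea-type event | Fall of ≥90% for ≥10 s | Both chest accelerometer signals fall ≥90% for more than 10 s |
| Hypopnea-type signal | Fall of ≥30% for ≥10 s | PAT attenuation (no percentage given) plus pulse rise ≥3 bpm within 15 s |
| Confirmation | ≥4% desaturation and/or arousal | ≥3% SpO2 fall within 60 s, or a snoring pause without that fall |
| Exclusions written out | None | Motion artifact, position change |
| Labels | Apneas and hypopneas, summed | One label |
| Denominator | TRT | TST, derived automatically from pulse rate |
| Cut-offs | 5, 15, 30 per hour | None |

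The apnea-type rules are close. The conflict lies in hypopnea-type events and the denominator.

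**Step 2: denominator.** I take TRT to be total recording time in minutes and read the formula as (apneas + hypopneas) × 60 / TRT. With r = TST/TRT, for the same events:

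TRT index = TST index × r, with r ≤ 1.

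The TST index is therefore never the lower of the two. The documents give no r, so the values below are assumptions. A TST index of 15/h corresponds to:
- r = 0.95: 15 × 0.95 = 14.25/h per TRT
- r = 0.90: 15 × 0.90 = 13.5/h per TRT
- r = 0.80: 15 × 0.80 = 12.0/h per TRT
- r = 0.60: 15 × 0.60 = 9.0/h per TRT

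At r = 0.80, anyone from 12.0 to just under 15.0/h per TRT is mild on TRT and moderate on TST. Assume a 480-minute recording with 384 minutes of sleep (384/480 = 0.80) and 100 events. The index is 100 × 60/480 = 12.5/h per TRT and 100 × 60/384 = 15.6/h per TST. In that recording every count from 96 (96 × 60/384 = 15.0) to 119 (119 × 60/480 = 14.875) is classified differently.

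**Step 3: event rule.** The differences pull in opposite directions. The 3% threshold and the snoring route admit events that the 4% limb does not. The required pulse rise, the motion and position exclusions, and the absence of an arousal route can remove events that Section 9.1 would count. One direction can be illustrated. Suppose an assumed 5% to 30% of the manual's events have a fall of 3% to under 4%, no arousal and no apnea-size drop, and Section 9.1 adds nothing in return. Then 15/h becomes 15 × 0.95 = 14.25/h to 15 × 0.70 = 10.5/h. The documents do not allow a net figure.

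**Step 4: brackets.** Read literally, the Section 9.1 formula divides only hypopneas by TRT. With an assumed 40 apneas and 60 hypopneas in 480 minutes, the literal result is 40 + 60 × 60/480 = 47.5; the bracketed result is 100 × 60/480 = 12.5. The bracketed form is evidently meant.

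**Step 5: effect per participant.** With 30 completers, one reclassified participant moves overall agreement by 1/30 = 3.3 percentage points. How many lie near 15/h is not stated.

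**The case against.** The best defence is that the texts work at two levels: Section 9.1 gives general definitions, names PAT as the substitute sensor and calls the result an estimate of AHI, while the manual turns this into steps for ANNE signals. That is a fair reading, and it tells a technician a good deal about how to mark events. It does not turn 4% into 3%, or TRT into TST. Nor does the separate name pAHI remove the conflict, because Section 9.1 applies its cut-offs to the ANNE value.

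Two further objections stand in part. The plan is descriptive, with no hypothesis test or performance target, and Section 10.3 lists Bland-Altman and severity-class accuracy as exploratory. That limits the weight of the point, but agreement is still a primary outcome. Also, text immediately before the manual is missing from the copy reviewed, so a linking or precedence statement cannot be excluded.

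A reader might infer more than the documents support:
- *That the manual's worked examples prove the conflict.* Section 3.3 labels seven events: five on PAT, pulse and a 3% fall, one on chest movement, and one on snoring with no 3% fall. That last event cannot meet the 4% limb, but it could qualify under Section 9.1 through an arousal or as an apnea, and so could the five. Neither drop sizes nor arousal status is given, so no event is shown to change status. The examples are illustrations only.
- *That ANNE records nothing from which an arousal could be identified.* Table 1 of the manual includes PAT and pulse rate, and the manual links PAT changes to arousals. What is missing is a scoring rule.
- *That Section 9.1 contradicts itself by listing "total sleep time (TST= the total amount of sleep time scored during the total recording time in minutes" as a scored variable.* Scoring TST does not make it the AHI denominator.
- *That the definition will be chosen after the WatchPAT results are seen.* The denominator could be changed by recalculation, but Section 9.1 states a formula and has scorers "blinded to the scoring of the HST". Nothing in the documents points to such a choice.

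**Conclusion.** The concern holds as a conflict between two written definitions of one classified index, and it should be corrected before scoring. Confidence is high for the textual conflict. It is not high for the absence of any precedence statement, given the missing text, or for the size of the effect.

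The denominator effect has a known direction: 15/h per TST equals 12.0 to 13.5/h per TRT at an assumed TST/TRT of 0.80 to 0.90, and 9.0 to 14.25/h over a wider assumed 0.60 to 0.95. The event-rule effect has no determinable net direction, so the documents do not support a claim that the manual inflates the index. The effect on agreement with WatchPAT ONE cannot be quantified, because Section 9.2 refers only to that device's operating manual.

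**What to change.** Before scoring starts:

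1. Reconcile Section 9.1 with Scoring Manual 3.1, 3.1.4 and 3.2 so that one event rule, one desaturation threshold and one denominator define the ANNE AHI on all four nights. Which rule to adopt is for the sponsor and investigators to decide.
2. Put brackets around the sum of apneas and hypopneas in the Section 9.1 formula.
3. Either state how an arousal is identified from the recorded ANNE signals, or make the text consistent without that criterion.
4. Report the night-one agreement table under the other denominator as a sensitivity analysis.

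The cost is wording in Section 9.1 and the manual plus one recalculated table. No new recordings and no re-reading are needed.

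Two additions are optional. Section 9.2 could record the threshold and denominator behind the WatchPAT index used, so that differences in definition are visible when agreement is interpreted. Night one could also be re-scored at a second desaturation threshold, at up to 30 × 3 = 90 reads for 30 completers and three scorers. The work per read may be less than a full read, because score sets begin from events already labelled by the software (manual, 3.1.2).

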8.1.3 ANNE™ Sleep procedures

The ANNE™ Sleep sensors will be applied by the study subjects themselves.

- 1) The PI or study coordinator will ensure the ANNE™ Sleep sensors are functional and collecting data properly prior to providing to subjects. The study coordinator will provide instructions for use of the ANNE™ Sleep system in the subject study kit.
- 2) Sensor placement (to be completed by the subject):
 - a) Using IPA alcohol wipes, the subject will wipe down the areas of the skin where the sensors will be placed thoroughly to remove any dirt, oils, etc. IPA alcohol wipes will also be used to clean the surface of the sensors before placement. If necessary, the subject may need to shave their chest to provide better adhesion and comfort of the sensor.
 - b) The subject will apply a single use adhesive to the chest sensor and place it on their chest at the suprasternal notch (see Figure 2). The subject will

STU#: STU00214445

attach the limb sensor to their finger using a single-use adhesive (see Figure 2).

[figure not shown]

Figure 2. Placement of the ANNE™ chest and limb sensors

3) Setting up a mobile device with an ANNE Sleep application

- a) The subject will pair the ANNE™ Chest and ANNE™ Limb sensors with the ANNE Sleep mobile application by following the instructions on mobile device
- b) After checking that the sensors are placed correctly and the signal quality is adequate, subjects will then proceed to sleep.

4) Data collection and storage

- a) After a full night of data collection, data will be collected through the ANNE Sleep application. The subject will download the data from the sensor through Bluetooth.
- b) The data will be uploaded automatically to ANNE™ Hub, a secure data repository from the application, and will be associated with the subject ID.
- c) The data will be stored in an EDF data format for further analysis.

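### The ANNE index has two denominators, recording time in protocol 9.1 and sleep time in the Scoring Manual, and nothing says which one is analysed

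*Combined protocol and SAP*

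**What the plan says.** Protocol 9.1 states: "Apnea-hypopnea index will be used to determine the presence and severity of sleep apnea". The formula beside it is "AHI = \text{apneas} + \text{hypopneas} * 60 / \text{TRT". TRT is missing from the abbreviation list and is not defined elsewhere in the supplied text; it is presumably the total recording time that 9.1 mentions when it defines TST. The section names the ANNE index only in the phrase "Sleep will be considered an estimation of AHI, coined as AHI", which gives a label and no denominator. It then sets the severity bands at 5, 15 and 30.

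The Scoring Manual, section 3.1 (Data Flow Overview), says: "pAHI (peripheral arterial tonometry AHI) is calculated by counting the number of sleep-disordered breathing events for the patient divided by the TST". It adds "TST is automatically calculated in ANNE Sleep Hub using pulse rate". On what happens after scoring, it says "the scored data is transferred back to the ANNE Sleep Hub for sleep report generation".

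Protocol 8.1.3 sends study recordings to the Hub and adds "The data will be stored in an EDF data format for further analysis". Sections 10.2 and 10.3 speak only of AHI. Section 9.2 leaves WatchPAT ONE scoring to its operating manual and states no denominator.

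**The concern.** Sleep time and recording time are different quantities: 9.1 itself defines TST as sleep scored within the recording. When part of the recording is spent awake, the protocol's index is lower than the manual's for the same events, so one night can be mild by the protocol and moderate by the manual.

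Two primary outcomes in section 4.1 use the index: night-one agreement on moderate to severe OSA, and between-night variation in AHI. The accuracy, sensitivity, specificity, predictive values and Bland-Altman analysis in 9.1 inherit it. If ANNE and WatchPAT ONE end up on different per-hour bases, part of any apparent device bias would come from the denominator alone. An open choice could also be settled after the results have been seen.

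**Working it through.** The plan gives no figure to reproduce, since this is a matter of definition. The cut-off of 15 (9.1), the four nights (8.1.2) and the minimum of 30 subjects (10.1) come from the documents. Every other input below is an assumption.

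**1. Relation between the indices.** For one event count, AHI(TRT) = AHI(TST) × r, where r = TST/TRT. A sleep-time AHI of 15 is a recording-time AHI of 15 × 0.90 = 13.5 or 15 × 0.75 = 11.25.

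**2. One recording.** Assume 110 events, TRT 480 min and TST 420 min.
- Protocol: 110 × 60/480 = 13.75, mild.
- Manual: 110 × 60/420 = 15.7, moderate.

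**3. Share of subjects who change class at 15.** Let the sleep-time AHI be log-normal with median m and geometric SD g. The share is P(15 ≤ X < 15/r) = Φ[ln(15/(r·m))/ln g] − Φ[ln(15/m)/ln g]. Take m from 12 to 20 and g from 2.0 to 2.5.

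| r | Upper limit 15/r | Share | Of 30 |
|---|---|---|---|
| 0.90 | 16.67 | 4.4–6.1% | 1.3–1.8 |
| 0.75 | 20 | 11.5–16.4% | 3.5–4.9 |

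Making the recording-time AHI log-normal instead, with limits 13.5–15 and 11.25–15, gives 4.3–6.1% and 11.2–16.4%.

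**4. Event counts may differ too.** For a hypopnea, 9.1 requires a drop of at least 4%: "oxygen desaturation from pre-event baseline and/or the event is associated with an arousal". The manual's section on detecting events has an accelerometer route close to the protocol's apnea rule. Its other routes need PAT attenuation and a pulse-rate rise, together with either an SpO2 drop of at least 3% or a snoring pattern. Let k be the manual's count divided by the protocol's. Then pAHI/AHI = k/r. With the protocol's AHI log-normal as in step 3:
- k = 0.8, r = 0.90: ratio 0.89; 4.9–6.8% cross 15 in the opposite direction.
- k = 0.9, r = 0.90: ratio 1.00; the two effects cancel and nobody crosses.
- k = 1.2, r = 0.75: ratio 1.60; 17.3–26.5% cross, or 5.2–8.0 of 30.

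**5. Between nights.** Take r = 0.75, 0.80, 0.85 and 0.90 over the four nights.
- Sleep-time AHI constant at 18: the recording-time values are 13.5, 14.4, 15.3 and 16.2 (mean 14.85, SD 1.16, CV 7.8%).
- Recording-time AHI constant at 12.5: the sleep-time values are 16.7, 15.6, 14.7 and 13.9 (mean 15.22, CV 7.9%).

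In each case one index shows no variation, while the other puts two nights on each side of 15. Which index looks steadier depends on the data.

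**6. Brackets.** Read literally, the printed formula applies 60/TRT only to hypopneas. With an assumed 40 apneas, 80 hypopneas and 480 min, it gives 40 + 80 × 60/480 = 50; with brackets it gives 120 × 60/480 = 15. This looks typographical, and the point does not rest on it.

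**The case against.** The best reply is that these are two indices for two purposes. The protocol gives one explicit study formula; the manual defines a differently named quantity for a report that a clinician reads. Sections 9 and 10 never mention pAHI, and 8.1.3 does not say that the Hub's index is analysed. So the documents do not prove that the wrong index will be used. That limit stands. But no supplied text states the two-purpose reading. The manual's declared purpose is to instruct those who score ANNE recordings, and its route through the Hub to EDF matches 8.1.3. Giving the protocol precedence would still leave TRT undefined and TST described in two ways: scored in 9.1, automatic from pulse rate in the manual.

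A second objection is that the sizes are largest where the assumed medians lie, close to 15. That is fair. With r = 0.90 and medians of 6 or 40, the same formula gives 2.3–2.8%, under 1 of 30. With r = 0.95 and medians 12–20 it gives 2.1–3.0%. A constant sleep-time AHI of 25 would give 18.75–22.5 over the four nights of step 5 and never cross 15.

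Third, no stated sample size, power or success threshold depends on the denominator, and the planned analyses are mainly descriptive. This is true, but those analyses still need a single definition of what they describe.

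Finally, one part of the public file and its figures were not available, so the absence of a reconciling statement refers to the text supplied.

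**Conclusion.** The concern holds. The file defines the per-hour ANNE index in two incompatible ways, and two of the three primary outcomes depend on which is used. The conflict is in the text; its size rests on assumptions. With equal counts and TST/TRT of 0.75–0.90, about 1 to 5 of 30 subjects change class at 15 if typical AHIs lie near that cut-off, and fewer if they lie well away from it or if little of the recording is spent awake. With counts differing by up to 20%, the range is 0–27% (0–8 of 30), because the numerator can offset or add to the denominator effect. If ANNE and WatchPAT ONE were on different bases, TST/TRT of 0.75–0.90 alone would produce a proportional difference of 10–25%. The direction cannot be known, since the WatchPAT ONE basis is not stated.

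**What to change.** Reconcile protocol 9.1 with Scoring Manual 3.1 before any ANNE and WatchPAT ONE results are compared:

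- Name one ANNE index, numerator and denominator, for the classification at 15, the Bland-Altman analysis and all four nights. Say whether it is the manual's pAHI.
- If the denominator is TST, give its single source. If it is TRT, define it and say how the value is obtained from the Hub data flow.
- State which event definition supplies the count: the one in 9.1 or the one in the manual's detection section.
- Print the formula with brackets: (apneas + hypopneas) × 60 / denominator in minutes, or total sleep-disordered breathing events × 60 / denominator in minutes. The second form matters because manual section 3.1.4 puts every event under one label, so that procedure does not yield separate apnea and hypopnea counts.
- In 9.2, state the WatchPAT ONE per-hour basis and, where its operating manual allows, use the same basis for both devices.
- Report the other ANNE index as a sensitivity analysis.

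The cost is one corrected formula and three or four sentences in 9.1 and 9.2. No new subjects or recordings are needed: both denominators relate to recordings already planned, and the Hub already computes TST.

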| Objectives: | 
Analysis of diagnostic yield from multiple nights with ANNE Sleep
 
 ● Analysis of agreement for diagnosis of moderate to severe OSA by determining a patient’s Apnea-Hypopnea Index (AHI) wearing the ANNE Sleep system and WatchPAT ONE over one (1) night worn concurrently ● Assessment of usability compared to current HST in the intended population |
| Investigational Product and Planned Use | ANNE™ Sleep System |
| Commercial Available HST Device | WatchPAT ONE |
| Statistical Analysis | Three subsequent nights will be with the ANNE Sleep system alone. Patient preference will be elicited via psychometric surveys for comfort |

STU#: STU00214445

| | |
|--|---|
| | 
and usability comparing ANNE and a commercially available Home Sleep Test (HST). We expect completion of this aim in 6 months. The apnea-hypopnea index (AHI) will be calculated in ranges of 15 – 30 apnea/hypopnea events per hour for moderate OSA and ≥ 30 apnea/hypopnea events per hour for severe OSA. The oxygen desaturation index (ODI), the hourly average number of desaturation episodes, will also be calculated. With a sample size of at least 30, the large amount of within-person data provides high statistical power for all planned analyses, allowing this data set to answer all proposed questions while minimizing study costs and any risk to patients.
 |
|--|---|

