9.2 WatchPAT ONE Scoring

The scoring method will be produced in accordance with the device operating manual.

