10.2 Apnea-hypopnea index (AHI) and oxygen desaturation index (ODI)

1. AHI will be calculated in ranges of 15 – 30 apnea/hypopnea events per hour for moderate OSA and ≥ 30 apnea/hypopnea events per hour for severe OSA. Continuous variables of AHIs during ~~three~~four-night study will be summarized using tables of descriptive statistics. The AHIs with variables will be summarized using counts and percentages. Descriptive statistics will be presented by diagnosis.
2. Diagnostic outcomes will be tabulated and compared for ANNE Sleep vs WatchPAT ONE.
3. Patient preference will be elicited via psychometric surveys for comfort and usability comparing ANNE and WatchPAT ONE.

STU#: STU00214445

4. The oxygen desaturation index (ODI), the hourly average number of desaturation episodes, will also be calculated.

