3.1.4 Adding Sleep Disordered Breathing Events

Drag the cursor on the **PAT signal** to label a sleep-disordered breathing event as **Obstructive Hypopnea**. Do not use other event types as the ANNE Sleep system will not distinguish differences among Obstructive Apnea, Hypopnea, and Central Apnea.

[figure not shown]

Figure 12: Enso Sleep Marked Events Scoring Screen

STU#: STU00214445

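### The AHI formula in protocol 9.1 lacks brackets and, read literally, adds a whole-night apnea count to an hourly hypopnea rate; this has no effect if every ANNE event carries the single hypopnea label, but the rule should be corrected and reconciled with the scoring manual

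*Combined protocol and SAP*

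**What the plan says.** Protocol 9.1 (ANNE Sleep Scoring) gives the index as "AHI = \text{apneas} + \text{hypopneas} * 60 / \text{TRT" and uses it for both presence and severity of sleep apnea. The same section defines apnea and hypopnea as distinct events and sets the classes, among them "AHI ≥ 5 – <15: Mild" and "AHI ≥ 30: Severe".

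The unit is stated elsewhere. Section 10.2 says "AHI will be calculated in ranges of 15 – 30 apnea/hypopnea events per hour for moderate OSA", and the Protocol Summary likewise speaks of "apnea/hypopnea events per hour for severe OSA".

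The ANNE scoring manual gives its own index. In 3.1 (Data Flow Overview), pAHI is "calculated by counting the number of sleep-disordered breathing events for the patient divided by the TST (total sleep time" in hours. In 3.1.4, scorers adding an event label it Obstructive Hypopnea, with the instruction "Do not use other event types as the ANNE Sleep system will not distinguish differences among Obstructive Apnea, Hypopnea, and Central Apnea". In 3.1.2, they begin from a score set that already holds events labelled by EnsoSleep; the types of those events are not stated.

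For the comparator, 9.2 says only: "The scoring method will be produced in accordance with the device operating manual".

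**The concern.** Multiplication and division come before addition, so the printed line means apneas + (hypopneas x 60 / TRT). The first term is a count for the night and the second is a rate per hour. Their sum is not in events per hour, which is the unit of the cut-offs at 5, 15 and 30.

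The ANNE AHI feeds two of the three primary outcomes in 4.1: variation between nights, and agreement with WatchPAT ONE on moderate to severe OSA. It also feeds the accuracy measures and the Bland-Altman plot. If the line were coded literally and some events were counted as apneas, the index would depend on how events were labelled as well as on how many there were. The error would fall on the ANNE side only, because WatchPAT ONE is scored by its own manual. The rule in 9.1 that sends a recording to a physician when scorers differ by more than 15% could also be triggered by labels alone.

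**Working it through.** The plan gives no worked AHI to reproduce, so the check compares the two readings directly.

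**Inputs.** The formula and classes come from 9.1, the per-hour unit from 10.2 and the Protocol Summary, and the single-label rule from manual 3.1.4. I take time in minutes, which fits the factor of 60 and the unit that 9.1 gives for total sleep time. The documents state no recording time or event mix, so those below are assumptions for illustration.

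**Formulas.** Let A be apneas, H hypopneas and T minutes.

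- As printed: A + H x 60 / T
- Bracketed: (A + H) x 60 / T
- Difference: A x (1 - 60 / T), which is zero when A = 0

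As printed, one apnea counts as much as T/60 hypopneas: 7 at T = 420 and 8 at T = 480.

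**Illustration at T = 420 minutes (assumed).**

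| A | H | Bracketed | As printed | Difference |
|---|---|---|---|---|
| 0 | 70 | 70 x 60/420 = 10.0 (mild) | 0 + 10.0 = 10.0 (mild) | 0 |
| 10 | 60 | 70 x 60/420 = 10.0 (mild) | 10 + 8.6 = 18.6 (moderate) | 8.6 |
| 30 | 60 | 90 x 60/420 = 12.9 (mild) | 30 + 8.6 = 38.6 (severe) | 25.7 |

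The first two rows hold the same 70 events. Two scorers who agreed on every event but labelled them in these two ways would differ by 8.6 on 10.0, well over 15%, under the printed formula. Under the bracketed one they would not differ at all.

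**How many apneas it takes.** For a night at a true 10/h, the printed value reaches 15 when A x (1 - 60/T) is at least 5. That takes 6 apneas at T = 360, 420 or 480. It reaches 30 when the same product is at least 20, which takes 24 apneas at 360 or 420 minutes and 23 at 480.

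**Under manual 3.1.4 (A = 0).** The two forms agree at every T. Eighty events give 80 x 60/360 = 13.3, 80 x 60/420 = 11.4 and 80 x 60/480 = 10.0 per hour under both. No night changes class.

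**The denominator.** Even with every event labelled a hypopnea, 9.1 divides by TRT and manual 3.1 by total sleep time. Eighty events over an assumed 480 minutes of recording give 10.0/h (mild). Over an assumed 300 minutes of sleep they give 80 x 60/300 = 16.0/h (moderate). The class changes once sleep time is 80 x 60/15 = 320 minutes or less.

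**The case against.** The strongest reply is that the harm does not arise when the study follows its own manual. Section 3.1.4 prescribes one label, and the detection steps in the manual's 3.2 recognise only one kind of sleep-disordered breathing event, so A = 0 and the printed formula already gives an hourly rate. The intent is not in doubt either: the cut-offs are per hour, AASM rules are invoked just before the formula, and pAHI puts all events in one numerator. The WatchPAT ONE index does not use the formula.

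Most of this stands, and it removes the stronger reading. A reader might infer from the table that the plan as written will move mild nights into the severe class. The documents do not support that: it needs both literal coding and a non-zero apnea count, and the manual tells scorers not to enter apneas. Nor does 9.1 instruct scorers to count apneas separately on ANNE recordings; it defines the two event types and so leaves that reading open. Nor is the line in 9.1 the only index formula, since pAHI is sound on this point.

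The objection does not make the printed rule correct. No section says whether 9.1 or the manual governs. The single-label instruction concerns events that a scorer adds, and nothing tells scorers to relabel those already in the starting score set. And if the apnea term is always zero, the formula in 9.1 misdescribes how the index is built.

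One caution: the point rests on punctuation. A bracket or a stacked fraction on the typeset page would settle the bracket question, though not the conflict with the manual.

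**Conclusion.** The formula is wrong as printed and contradicts the unit of its own cut-offs. Its effect in this study runs from nil, if all ANNE events carry the single label, to a change of class if apneas are counted separately or pre-labelled events keep an apnea type, and the line is coded literally. The documents do not show how likely the second case is, and every non-zero figure above rests on an assumed recording time and event mix. The weight is therefore minor. It still merits correction, because this is the operative definition of the index behind two primary outcomes. The denominator conflict on the same line can change a class even under single-label scoring and should be settled in the same edit.

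**What to change.** - In 9.1, write AHI = (apneas + hypopneas) x 60 / T, with T in minutes.
- State that all sleep-disordered breathing events in the final score set enter the bracket whatever their label, including pre-labelled EnsoSleep events that the scorer keeps.
- Reconcile 9.1 with manual 3.1 and 3.1.4. Say whether the analysed index is the protocol's AHI or the manual's pAHI, define T once as total recording time or total sleep time, and say how the separate event definitions in 9.1 relate to the single label.
- Confirm which event types the starting score set contains, and check the analysis code against one hand-worked recording.

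The cost is a short text amendment and a brief code check. Data collection does not change.
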